7.4.1 Serious Adverse Event Detection and Reporting

All serious adverse events will be:

- recorded on the appropriate serious adverse event report form
- followed through resolution by a study physician
- reviewed by a study physician

Any AE considered serious by the Principal Investigator or Subinvestigator or which meets the aforementioned criteria must be submitted on an SAE form to PPD Development, NIAID's pharmacovigilance contractor, at the following address:

Medical Affairs/Pharmacovigilance

PPD Development

[name]

Wilmington, NC 28412

SAE Fax line: [contact]

Questions about SAE reporting can be referred to the SAE Hotline (available 24 hours a day/7 days a week) at [contact]

The study clinician will complete a Serious Adverse Event Form within the following timelines:

- All deaths, and all life-threatening events regardless of relationship, will be recorded on the Serious Event Form and sent by fax within 24 hours of site awareness of the death or life-threatening event.
- All other serious adverse events, regardless of relationship, will be reported via fax by the site within 72 hours of becoming aware of the event.

Other supporting documentation of the event may be requested by the pharmacovigilance contractor and should be provided as soon as possible.

All SAEs will be followed until satisfactory resolution or until the Principal Investigator or Subinvestigator deems the event to be chronic or the patient to be stable.

REGULATORY REPORTING FOR STUDIES CONDUCTED UNDER DMID SPONSORED IND

Following notification from the investigator, DMID, the IND sponsor, will report events that are both serious and unexpected that are related to study product(s) to the FDA within the required timelines as specified in 21 CFR 312.32: fatal and life threatening events within 7 calendar days (by phone or fax). All written reports will be sent within 15 calendar days. All serious events designed as "not related" to study product(s), will be reported to the FDA at least annually in a summary format.

REPORTING OF ADVERSE EVENTS TO THE NIAID IRB

Any AE considered serious by the Principal Investigator or Subinvestigator or which meets the aforementioned criteria will also be reported to the University of Rochester IRB and the NIAID IRB at [contact]. A summary of data will be provided. Additionally, all Grade 3

and 4 adverse events that are determined to be associated with vaccination will be reported to the NIAID IRB within 15 days of the NIH investigator becoming aware of such events.

7.4.2 Reporting of Pregnancy

Pregnancies occurring in study participants will be reported by fax to the medical affairs/pharmacovigilance contractor at the address above. No further vaccinations will be administered to pregnant volunteers, but all study mandated blood samples will be obtained and the subject will continue in follow-up for safety events. Pregnancies will be followed for pregnancy outcome.

7.5 PROCEDURES TO BE FOLLOWED IN THE EVENT OF ABNORMAL LABORATORY TEST VALUES OR ABNORMAL CLINICAL FINDINGS

Laboratory Test Values: All laboratory test abnormalities will be reported to PPD and followed to resolution. The clinical significance of laboratory abnormalities will be assessed with appropriate referral for further workup as needed.

7.5.1 Procedures for subjects developing moderate or greater anemia

Subjects who develop decreased Hgb levels or changes in Hgb levels corresponding to toxicities graded as moderately severe or greater according to section 17.3 will have the following procedures:

- A workup, consisting of reticulocyte count, total iron binding capacity (TIBC), ferritin, direct Coombs test, haptoglobin level, total and direct bilirubin, and lactic acid dehydrogenase.
- Subjects found to be iron deficient will forgo further blood drawing for T cell (20 mL), B cell (10 mL) and GIA (20 mL) assays. Immunizations will continue and samples for laboratory safety tests and anti-AMA1 antibody will be obtained per schedule
- Subjects found to have autoimmune hemolytic anemia will not receive further doses of vaccine.

7.6 TYPE AND DURATION OF THE FOLLOW-UP OF SUBJECTS AFTER ADVERSE EVENTS

Adverse events will be followed until resolved or considered stable.

7.7 HALTING RULES

A Safety Monitoring Committee (SMC) will be asked to review cumulative safety data up to and including day 35 post-vaccination prior to dose escalation of the next cohort. If a dose of

vaccine is considered unacceptably reactogenic, dose escalation and/or additional vaccinations will be suspended until reviewed with the Safety Monitoring Committee and study sponsor. This decision will also be reported to the NIAID IRB. The SMC will adhere to DMID guidelines. If none of the above conditions occur, dose escalation will proceed.

The following criteria will be used to define unacceptable reactogenicity of the AMA1-C1/Alhydrogel[®] + CPG 7909 malaria vaccine:

1. One or more volunteers experience a Serious Adverse Event (SAE) that is determined to be associated (unlikely, possibly, probably, or definitely related) to the vaccination, OR
2. One or more volunteers experience anaphylaxis that is associated (unlikely, possibly, probably or definitely related) to the vaccine, OR
3. Any severe clinical illness occurs that is not explained by a diagnosis that is unrelated to vaccination, OR
4. One or more volunteers in a single-dose cohort experience an objective physical finding or laboratory abnormality of Grade 3 or higher, OR
5. Two or more volunteers in a single dose cohort experience a Grade 2 or higher laboratory abnormality or Grade 3 clinical AE.

The NIAID IRB will be notified of the decision to halt or to continue vaccinations within one working day of the NIH investigator becoming aware of such events.

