4.1 INCLUSION CRITERIA

- 4.1.1 Age between 18 and 45 years, inclusive.
- 4.1.2 Good general health as a result of review of medical history and/or clinical tests.
- 4.1.3 Available for the duration of the trial (34 weeks).
- 4.1.4 Willingness to participate in the study as evidenced by signing the informed consent document.

4.2 EXCLUSION CRITERIA:

- 4.2.1 Pregnancy as determined by a positive urine β -hCG (if female) at any point during the study.
- 4.2.2 Participant unwilling to use highly effective contraception methods (such as: abstinence, birth control pills or birth control patches or vaginal ring, diaphragm with spermicide, IUD (intrauterine device), condom with spermicide, progestin implant or injection, surgical sterilization (hysterectomy, bilateral oophorectomy, tubal ligation), or a partner who has had a vasectomy) for the duration of the trial (if female).
- 4.2.3 Currently lactating and breast-feeding (if female).
- 4.2.4 Evidence of clinically significant immunosuppressive, neurologic, cardiac, pulmonary, hepatic, rheumatologic, autoimmune, or renal disease by history,

physical examination, and/or laboratory studies including urinalysis (see Appendix 17.3).

- 4.2.5 Behavioral, cognitive, or psychiatric disease that in the opinion of the investigator affects the ability of the volunteer to understand and cooperate with the study protocol.
- 4.2.6 Laboratory evidence of liver disease (aspartate aminotransferase greater than 1.25 times the upper limit of normal of the testing laboratory).
- 4.2.7 Laboratory evidence of renal disease (serum creatinine greater than the upper limit of normal of the testing laboratory).
- 4.2.8 Laboratory evidence of hematologic disease (absolute neutrophil count $<1,500/\text{mm}^3$; hemoglobin < 0.9 times the lower limit of normal of the testing laboratory, by sex; or platelet count $<140,000/\text{mm}^3$).
- 4.2.9 Other condition that in the opinion of the investigator would jeopardize the safety or rights of a volunteer participating in the trial or would render the subject unable to comply with the protocol.
- 4.2.10 Participation in another investigational vaccine or drug trial within 30 days of starting this study, or while this study is ongoing.
- 4.2.11 Volunteer has had medical, occupational, or family problems as a result of alcohol or illicit drug use during the past 12 months.
- 4.2.12 History of a severe allergic reaction or anaphylaxis.

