5.22 STUDY EVENTS FLOW SHEET

The following table summarizes the events in the study, and estimates the total volumes of blood drawn at each visit and in total.

			V1	V2	V3	V4	V5	V6	V7	V8	V9	V10	V11	V12	V13	V14	V15
	BV*	Pre	0	3	7	14	28	31	35	42	56	59	63	70	84	140	236
Hx and Exam		X															
Informed consent		X															
Interim Hx, Exam			X	X	X	X	X	X	X	X	X	X	X	X	X	X	X
CBC & differential**	5	X	X	X	X	X	X	X	X	X	X	X	X	X	X	X	X
Chemistries	5	X	X	X		X	X	X		X	X	X		X			
Urinalysis		X	X			X	X			X	X			X	X		X
Urine pregnancy***		X	X				X				X						
HIV, HBV, HCV	10	X															
RF, Anti-dsDNA, ANA	5	X	X		X		X		X		X		X		X		X
C3, C4, CH50	5		X														
VACCINATION			X				X				X						
Anti-AMA1 antibody	10		X			X	X			X	X			X	X	X	X
GIA	20		X							X	X			X			X
B cell analysis	20		X	X	X		X	X	X		X	X	X	X	X	X	X
T cell analysis	10		X	X	X		X	X	X		X	X	X	X	X	X	X
Total Blood (mL) drawn		25	80	40	40	20	55	40	40	40	75	40	40	70	50	45	70

* - BV = Blood volume (mL) required for test. Total volume drawn over course of study is 770 mL.

** - CBC parameters to be assessed for safety: WBC, Hemoglobin, Platelet count,

*** - Female subjects only

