7.4 REPORTING PROCEDURES

Adverse Events including local and systemic reactions not meeting the criteria for “serious adverse events” will be captured on the appropriate case report form. Information to be collected includes event description, date of onset, investigator assessment of severity, relationship to study product, date of resolution of the event, seriousness, and outcome. All adverse events occurring while on study will be documented appropriately regardless of relationship. All AEs will be followed to adequate resolution.

Any medical condition that is present at the time that the patient is screened will be considered as baseline and not reported as an AE. If the severity of any preexisting medical condition increases during the study period, then it will be recorded as an AE.

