17.3 TOXICITY GRADING SCALE FOR LABORATORY ADVERSE EVENTS

Laboratory	Mild (Grade 1)	Moderate (Grade 2)	Severe (Grade 3)
Hgb (♀) – gm/dl	< 11.5 & ≥ 11.0	< 11.0 & ≥ 10.0	< 10.0
Hgb (♀) – change from baseline value in gm/dl	≥ 1.0 & < 1.5	≥ 1.5 & < 2.0	≥ 2.0
Hgb (♂) – gm/dl	< 12.5 & ≥ 12.0	< 12.0 & ≥ 11.0	< 11.0
Hgb (♂) – change from baseline value in gm/dl	≥ 1.5 & < 2.0	≥ 2.0 & < 2.5	≥ 2.5
WBC – cells/mm ³ (Increase in WBC)	≥ 11000 & < 15000	≥ 15000 & < 20000	≥ 20000
WBC – cells/mm ³ (Decrease in WBC)	< 3500 & ≥ 2500	< 2500 & ≥ 1500	< 1500
Platelets – cell/mm ³	< 135,000 & ≥ 125,000	< 125,000 & ≥ 100,000	< 100,000
AST/ALT (increase by factor)	> 1.0 & < 2.5 x ULN	≥ 2.5 & < 4 x ULN	≥ 4 x ULN
Serum creatinine – mg/dL	IN* - IN+0.2	> IN+0.2 - < 2.0	≥ 2.0

URINALYSIS				
	Grade 1	Grade 2	Grade 3	Grade 4
Proteinuria	2+ or 0.5 - 1 gm loss/day	3+ or 1 - 2 gm loss/day	4+ or 2 - 3.5 gm loss/day	nephrotic syndrome or > 3.5 gm loss/day
Hematuria	5-10 rbc/hpf	>10 rbc/hpf	gross, with or without clots, OR red blood cell casts	requires hospitalization

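### Hemoglobin: depending on the laboratory's normal range, 4.2.8 can admit volunteers already at Grade 2, and a fall that 17.3 leaves ungraded as a change can then meet a one-volunteer halting criterion

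*Protocol*

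**What the plan says.** **Entry (Protocol 4.2.8).** The hemoglobin exclusion is relative: "hemoglobin < 0.9 times the lower limit of normal of the testing laboratory, by sex". The LLN itself is not stated.

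**Grading (Appendix 17.3).** Hemoglobin is graded in two ways. The absolute rows use fixed values in g/dL:
- women: Grade 1 from 11.0 to below 11.5, Grade 2 from 10.0 to below 11.0, Grade 3 below 10.0;
- men: Grade 1 from 12.0 to below 12.5, Grade 2 from 11.0 to below 12.0, Grade 3 below 11.0.

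A second row for each sex grades "change from baseline value in gm/dl". It starts at 1.0 (women) and 1.5 (men), with Grade 2 from 1.5 and 2.0. The appendix does not rank the two rows.

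**Halting (7.7).** Criterion 4: "One or more volunteers in a single-dose cohort experience an objective physical finding or laboratory abnormality of Grade 3 or higher". Criterion 5: "Two or more volunteers in a single dose cohort experience a Grade 2 or higher laboratory abnormality or Grade 3 clinical AE". Criteria 1 and 2 require association with vaccination, and criterion 3 excuses illness with an unrelated explanation. Criteria 4 and 5 carry no condition on baseline, change or cause.

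**Related rules.** Section 7.4 treats conditions present at screening as baseline for AE reporting, but adds: "If the severity of any preexisting medical condition increases during the study period, then it will be recorded as an AE". Section 7.5.1 orders a work-up for "Subjects who develop decreased Hgb levels or changes in Hgb levels corresponding to toxicities graded as moderately severe or greater according to section 17.3" and lets iron-deficient subjects continue immunization. The flow sheet in 5.22 states: "Total volume drawn over course of study is 770 mL".

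**The concern.** A floor that moves with the laboratory is set against fixed grade limits, and nothing ties the two together. A volunteer whom 4.2.8 accepts may already sit in Grade 2, close above the Grade 3 limit. A small drift, well within what repeated blood draws might produce, then gives an absolute Grade 3, and criterion 4 needs only one such person. The vaccine with CPG 7909 would be labelled unacceptably reactogenic, and escalation or dosing paused, on a change that the protocol's own change row does not grade. The same floor also places already anemic healthy volunteers in a heavy sampling schedule. Study endpoints are not affected.

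**Working it through.** **1. The protocol's own figure.** The visit volumes in 5.22 add up: 25+80+40+40+20+55+40+40+40+75+40+40+70+50+45+70 = 770 mL, as stated. Screening through Day 35, the review point for escalation, is 25+80+40+40+20+55+40+40 = 340 mL.

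**2. When can a volunteer enter already graded?** The lowest admitted value is 0.9 x LLN (4.2.8). Compare it with the absolute limits in 17.3:
- entry at Grade 2: LLN < 11.0/0.9 = 12.22 (women) or < 12.0/0.9 = 13.33 (men);
- entry at Grade 3: LLN < 10.0/0.9 = 11.11 (women) or < 11.0/0.9 = 12.22 (men).

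If the upper Grade 1 bounds of 17.3 (11.5 and 12.5) are taken as the LLN, the floors are 10.35 and 11.25, both Grade 2.

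**3. When can an ungraded fall reach Grade 3?** The change row is silent below 1.0 (women) and 1.5 (men):
- women: 0.9 x LLN - 10.0 < 1.0, so LLN < 11.0/0.9 = 12.22;
- men: 0.9 x LLN - 11.0 < 1.5, so LLN < 12.5/0.9 = 13.89.

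These are exact limits. With values reported to 0.1 g/dL, Grade 3 starts at 9.9 and 10.9 and the largest ungraded falls are 0.9 and 1.4. The starting value must then be at most 10.8 or 12.3, that is LLN at most 10.8/0.9 = 12.0 or 12.3/0.9 = 13.67.

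**4. Range over assumed LLNs.** The fall runs from the lowest eligible value, at 0.1 g/dL resolution, to 9.9 (women) or 10.9 (men).

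| Sex | Assumed LLN | 0.9 x LLN | Grade at that value | Fall to Grade 3 | Change-row grade |
|---|---|---|---|---|---|
| Women | 11.5 | 10.35 | 2 | 0.5 | none |
| Women | 12.0 | 10.80 | 2 | 0.9 | none |
| Women | 12.5 | 11.25 | 1 | 1.4 | 1 |
| Men | 12.5 | 11.25 | 2 | 0.4 | none |
| Men | 13.0 | 11.70 | 2 | 0.8 | none |
| Men | 13.5 | 12.15 | 1 | 1.3 | none |
| Men | 14.0 | 12.60 | ungraded | 1.7 | 1 |

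**5. Other parameters.** No other test with both a numeric entry limit and a grade in 17.3 allows entry at Grade 2. Platelets are excluded below 140,000, above the Grade 1 limit of 135,000. AST is excluded above 1.25 x ULN, while Grade 2 starts at 2.5 x ULN. Creatinine is excluded above the ULN.

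**The case against.** **An entry value is not a halting event.** Appendix 17.3 is titled as a scale for laboratory adverse events, 7.3.1 counts an abnormal laboratory finding as a possible AE, and 7.4 takes screening conditions as baseline. Section 7.7 speaks of volunteers experiencing an abnormality and defines reactogenicity of the vaccine. On that reading an unchanged pre-dose Grade 2 does not count. Much of this stands: two unchanged entry values could count toward criterion 5 only because 7.7 has no explicit baseline condition and does not refer to 7.4. It does not touch the fall from Grade 2 to Grade 3, since 7.4 itself records worsening.

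**Pausing for a fall to 9.9 g/dL is prudent.** The adjuvant carries an autoimmunity concern, and 7.5.1 looks for hemolysis. Section 7.5.1 also acts on either a low level or a change, so the two rows read naturally as alternative triggers. This stands. The rows do not contradict each other, and the objection to the rule is its poor specificity in someone admitted near the limit.

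**Admission is not automatic and sampling can be cut.** Sections 4.1.2 and 4.2.9 leave room for judgment. Section 7.5.1 drops the B-cell, T-cell and GIA draws in iron deficiency. Through Day 35 these are 6 x 30 + 20 = 200 of the 340 mL. This stands in part: judgment sets no limit, 4.2.4 points to 17.3 but does not list hematologic disease, and the relief starts only after moderate anemia has led to a work-up that finds iron deficiency.

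**Conclusion.** The mismatch is real but conditional, and its severity is minor. It rests on the testing laboratory's LLN being below 12.22 g/dL (women) or 13.33 g/dL (men) for entry at Grade 2, and below 12.22 or 13.89 for an ungraded fall to reach Grade 3. The protocol does not give the LLN, and at higher values these routes close.

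Three stronger readings are not supported:
- A reader might infer that entry values alone can meet criterion 4. That needs entry at Grade 3, hence an LLN below 11.11 or 12.22.
- A reader might infer that a false halt is likely. The protocol gives neither the LLN nor a distribution of hemoglobin among volunteers, so any halting probability would rest on an invented rate.
- A reader might infer that the trial would stop. Section 7.7 suspends only pending review by the Safety Monitoring Committee and the sponsor.

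What is left is an avoidable pause and an avoidable sampling burden on anemic volunteers.

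**What to change.** **(1) Section 4.2.8.** Exclude hemoglobin below 11.5 g/dL in women or 12.5 g/dL in men, or below 0.9 x LLN if that is higher. No one is then eligible at screening with a graded value. Grade 3 then needs a fall of more than 11.5 - 10.0 = 1.5 (women) or 12.5 - 11.0 = 1.5 g/dL (men). The change row already grades such a fall as at least 2 (women) or 1 (men).

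**(2) Section 7.7.** State that a hemoglobin grade counts toward criteria 4 and 5 only if it is higher than the grade of the Day 0 pre-dose sample, or if the change row gives it. Only an unchanged entry grade stops counting. No judgment of cause is added.

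**Cost.** Amended wording and a few more screen failures; with an LLN of 12.0, for example, women from 10.8 to 11.4 g/dL would no longer qualify. No new tests are needed, since hematology is already drawn at screening and Day 0.

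**What remains.** A fall of 0.6 g/dL, from 11.5 to 10.9 or from 12.5 to 11.9, is ungraded as a change but reaches absolute Grade 2, so two such volunteers still meet criterion 5. Closing that too would need floors of 11.0 + 1.0 = 12.0 and 12.0 + 1.5 = 13.5 g/dL. A two-volunteer trigger of this kind is acceptable as a conservative rule. Screening may also precede dosing by up to 56 days, so a volunteer can drift into a grade by Day 0. Part (2) then discounts that grade while it is unchanged, but a further worsening still counts.

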1.4 KNOWN AND POTENTIAL RISKS AND BENEFITS

Possible local vaccine reactions include pain, swelling, erythema, induration, limitation of limb movement for several days, lymphadenopathy, or pruritus at the injection site. Local SC nodules, believed to be granulomatous reactions to aluminum hydroxide, have been observed with use of aluminum hydroxide-based adjuvants. Thus, most aluminum hydroxide-adsorbed vaccines are injected IM rather than SC. Systemic reactions such as fever, chills, headache, fatigue, malaise, myalgia, joint pain, may also possibly occur. Immediate hypersensitivity reactions including urticaria, anaphylaxis, or other IgE mediated responses are possible as with any vaccine.

CPG 7909 is a potent immune activator, and has the potential to overcome the normal tolerance of the immune system for self antigens. In a number of murine models, administration of CPG 7909 has been associated with development of certain autoimmune phenomenon (see Coley Investigator Brochure, Appendix 3). However, the relevance of this finding to humans is unclear because while TLR-9 receptors are widely distributed among immune cells in mice, they appear to be restricted to B cells and plasmacytoid dendritic cells in humans. No subject in any study to date with CPG 7909 oligonucleotides has developed signs or symptoms of autoimmune disease.

In animal studies, CPG 7909 oligodeoxynucleotides (ODN) given by themselves only rarely induce the production of anti-dsDNA antibodies. However, if the CPG 7909 ODN are administered as a complex together with a foreign protein or other antigen that can elicit T cell help, then it is likely that antibodies against the CPG 7909 ODN will be produced, and these

may cross-react with dsDNA. Vaccination of humans with a CPG 7909 ODN together with an antigen capable of binding to the ODN could be expected to result in the production of IgG anti-ODN antibodies, which could cross react with self DNA.

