7.2 METHODS AND TIMING OF SAFETY ASSESSMENTS

Subjects will be asked to keep daily symptom diaries recording oral temperature once daily, as well as pain, tenderness, redness, and induration at the injection site for six days

following each immunization. The size of any injection site reaction will be measured utilizing a standardized clear plastic measurement device and recorded in the volunteer symptom diary. See Appendix 17.4.

Using standard techniques, the clinical laboratory, will perform the following tests:

1. Complete blood count plus white blood cell differential (parameters to be assessed for safety: WBC, Platelet count, Hemoglobin)
2. Serum creatinine
3. Aspartate aminotransferase (AST)
4. Urinalysis (in the event of an abnormal urine dipstick test)
5. Rheumatoid factor - laboratory cut-off for negative results = "negative"
6. Anti-dsDNA (ELISA) – laboratory cut-off for negative result < 1:4
7. ANA – laboratory cut-off for negative result \leq 1:80
8. C3
9. C4

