7.3.2 Reactogenicity Grading Scale

The grading scales for solicited clinical reactions, and for laboratory abnormalities, are given in appendix 17.2 and 17.3. Unsolicited clinical reactions will be graded according to appendix 17.5.

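### The laboratory halting criteria in 7.7 work only through grades, and Appendix 17.3 has none for anti-dsDNA, ANA or RF, so no number of asymptomatic anti-dsDNA conversions triggers a pause by rule

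*Protocol*

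**What the plan says.** Section 7.7 introduces five conditions with "The following criteria will be used to define unacceptable reactogenicity". Criteria 1 to 3 need an associated serious adverse event (SAE), anaphylaxis, or a severe clinical illness without an unrelated diagnosis. Criterion 4 needs one Grade 3 physical finding or laboratory result. Criterion 5 reads "Two or more volunteers in a single dose cohort experience a Grade 2 or higher laboratory abnormality or Grade 3 clinical AE". The stated default is "If none of the above conditions occur, dose escalation will proceed".

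On grading, 7.3.2 says "The grading scales for solicited clinical reactions, and for laboratory abnormalities, are given in appendix 17.2 and 17.3". Appendix 17.3, headed "TOXICITY GRADING SCALE FOR LABORATORY ADVERSE EVENTS", covers haemoglobin (level and "change from baseline value in gm/dl"), white cells, platelets, AST/ALT, creatinine, proteinuria and haematuria. It has no row for anti-dsDNA, ANA or RF.

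Section 7.2 lists these three as safety tests and gives only a limit for a negative result, for anti-dsDNA "laboratory cut-off for negative result < 1:4". They are drawn on Day 0 and on Days 7, 28, 35, 56, 63, 84 and 236 (5.5 to 5.19 and the 5.22 flow sheet). Section 1.4 explains why: "CPG 7909 is a potent immune activator, and has the potential to overcome the normal tolerance of the immune system for self antigens". Under 4.4.2(4), anti-dsDNA stops further doses in a subject only when ANA has also become positive.

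**The concern.** The adjuvant's named laboratory risk is autoantibody induction, and the protocol pays for eight draws per subject to look for it after screening. Yet the rule that decides whether escalation or further vaccination is suspended cannot read the result, because it reads laboratory findings only through a grade and these tests have none. A pause would depend on SMC discretion, or on an intensity that an investigator assigns case by case under 7.3.1 with no scale behind it.

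The contrast with ordinary laboratory findings is sharp. Two women in a cohort whose haemoglobin falls by 1.5 g/dl (Grade 2 in 17.3) meet criterion 5. Fifteen of 15 CPG 7909 recipients with isolated, asymptomatic anti-dsDNA meet no criterion by a defined grade. At stake is the safety of healthy volunteers due a further dose, and of the cohort waiting to open.

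**Working it through.** **1. The protocol's own figure.** Section 9.4 gives about 0.8 as the chance of seeing at least one event at rate 0.1 in 15 subjects: 1 − 0.9^15 = 0.794. It reproduces. The point here disputes no stated figure.

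**2. Tracing the protocol's own precedent.** Section 1.2.4 describes one recipient of hepatitis B vaccine with 1.0 mg CPG 7909 who had raised anti-dsDNA, no symptoms, and negative ANA and RF throughout.

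| Rule | Met by this pattern? |
|---|---|
| 7.7 criterion 1 (associated SAE) | Not ordinarily: asymptomatic |
| 7.7 criterion 2 (anaphylaxis) | No |
| 7.7 criterion 3 (severe clinical illness) | No |
| 7.7 criteria 4 and 5 (laboratory grade) | No grade exists in 17.3 |
| 4.4.2(4) (individual stop) | No: ANA not newly positive |

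Nothing changes if two, five or fifteen subjects in a cohort show it, since only criterion 5 counts subjects and it counts grades.

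**3. How often a two-subject threshold would be reached.** Inputs: n = 15 CPG 7909 recipients in each cohort (3.2). The conversion rate p in this trial is unknown, so p is assumed over a range: 1/56 = 1.8% (one case in the 56-subject hepatitis B trial; the number given CPG 7909 is not stated), 5%, 10%, and 27/155 = 17.4% (1.4, antineoplastic use).

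P(≥2) = 1 − (1 − p)^15 − 15p(1 − p)^14. For p = 0.10: 1 − 0.206 − 0.343 = 0.451. Chance that at least one of Cohorts 1 and 2 reaches two, with the same rate in both: 1 − (1 − P)^2.

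| Assumed p | One cohort | At least one of Cohorts 1 and 2 |
|---|---|---|
| 1.8% | 2.9% | 5.7% |
| 5% | 17% | 31% |
| 10% | 45% | 70% |
| 17.4% | 76% | 94% |

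These take conversion at any post-dose draw. The Day 35 review sees only Days 7, 28 and 35, so the chance by then may be lower.

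**4. Cost of a trigger.** The protocol gives no background rate. With the same formula, if 1%, 2% or 5% of subjects turned positive by chance, 1.0%, 3.5% or 17% of cohorts with 15 CPG 7909 recipients would meet the criterion.

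**5. Timing.** In 13.5 the SMC reviews Day 7 and Day 35 data of Stages 1 and 2. Section 3.2 adds all available Cohort 1 data before Cohort 3 opens. No SMC review is scheduled between Day 35 and the third dose on Day 56, or within Cohort 3.

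**The case against.** The strongest reply is that oversight is already in place. Abnormal laboratory tests by group are a safety endpoint (3.1.1). All laboratory abnormalities are reported, assessed and followed (7.5). The SMC sees the Day 7, 28 and 35 autoantibody results before each cohort opens. Haematologic and renal consequences of autoimmunity are graded in 17.3, and 7.5.1 adds a Coombs test and stops dosing for autoimmune haemolysis. All of this stands, and it rules out the inference that the protocol leaves autoantibodies unmonitored. Nor does the default to escalate bind the SMC, whose recommendation in 13.5 is not limited to the five criteria. But none of these provisions sets a cohort-level trigger.

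A second reply is that the sponsor took a position: 4.4.2(4) does not stop even one subject for isolated anti-dsDNA, and 1.4 says such antibodies have generally declined and are of unknown significance. This argues against stopping the trial. It argues less against a pause to look at a cluster, which one subject's result cannot show. It does weigh against triggering on ANA or RF alone, a debatable threshold not proposed here.

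A reader might also infer that the severity-classified primary safety endpoint in 9.2.1 cannot register a conversion. The documents do not settle that. Section 7.3.2 assigns Appendix 17.5 to unsolicited clinical reactions, but its title covers unsolicited adverse events generally and its contents are not in the text at hand.

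Finally, the precedent was first detected two weeks after the second dose. That corresponds to Day 42 here, after the Day 35 review and at a visit with no autoantibody draw. This stands as a limit on any trigger built on the existing draws, and it is a reason not to confine the trigger to data up to Day 35.

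**Conclusion.** The point holds for halting criteria 4 and 5: with no grade in 17.3, asymptomatic anti-dsDNA conversion has no defined route to a rule-based pause at any frequency, and the isolated form also misses the individual stop. This rests on the text alone. Its practical size rests on assumed conversion rates: two or more converters in a cohort would be uncommon at 1.8% (2.9%) and likely at 17.4% (76%). The upper rate comes from a different population and exposure and may overstate the risk in healthy vaccinees. Because SMC review softens the gap, this is a change the sponsor should make rather than a fault that invalidates the design.

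**What to change.** Add to 7.7 a criterion that needs no grade: if two or more CPG 7909 recipients in a cohort change from anti-dsDNA negative on Day 0 to positive (not below 1:4, the 7.2 limit) at any post-dose draw, including after Day 35 and in Cohort 3, escalation and further vaccinations are suspended until the SMC has reviewed the anti-dsDNA, ANA and RF results by arm.

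The cost is wording, with no new samples or visits. Exclusion 4.2.24 and the Day 0 draw already supply a negative baseline. Section 3.3 blinds only the subjects and the codes sit in the enrollment module (5.3), so the Data Coordinating Center can count by arm without breaking the stated blind. There are two downsides. Sporadic low-titre conversions may prompt reviews, in about 1% to 17% of cohorts if the background rate is 1% to 5% (assumed). A short rise two weeks after a dose may still be missed, because through Day 84 the post-dose draws fall 7 and 28 days after each dose.
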